Grade 1: Creatinine >ULN to ≤1.5x ULN	 Monitor creatinine weekly Rule-out other causes (e.g. fluids, medications, i.v. contrast) Promote hydration and cessation of nephrotoxic drugs 	Continue spartalizumab/LAG525 treatment
Grade 2: Creatinine >1.5 - 3.0 x baseline; >1.5 to ≤ 3.0 x ULN	 Monitor creatinine every 2 to 3 days and consult with nephrologist Rule-out other causes (e.g. fluids, medications, i.v.contrast) 	Interrupt spartalizumab/LAG525 until serum creatinine recovers to ≤ Grade 1 or baseline

Nephritis (NCI-CTCAE v5.0)		
Grade	Recommended Adverse Event management guidelines	Mandatory Dose Modification requirements
	 Initiate 0.5 to 1 mg/kg/day prednisone or equivalents if other causes are ruled out If worsening or no improvement: 1 to 2 mg/kg/day prednisone equivalents Promote hydration and cessation of nephrotoxic drugs Consider renal biopsy 	
Grade 3: Creatinine >3.0 x baseline; >3.0 to <6 x ULN	 Monitor creatinine every 1 to 2 days and consider hospitalization Consult with nephrologist and consider renal biopsy Start 1 to 2 mg/kg/day prednisone equivalents Once event improves to Grade ≤1, slowly taper steroids over at least 4-6 weeks 	Permanently discontinue spartalizumab/LAG525
Grade 4: Creatinine > 6.0 x ULN	 Same as Grade 3 hospital for close monitoring and management as per institutional guidelines 	Permanently discontinue spartalizumab/LAG525

^{*}In participants with impaired renal function, dosage of carboplatin should be reduced as per local labeling for carboplatin and hematologic nadirs and renal function monitored.

Table 6-7 Criteria for dose interruption and re-initiation of LAG525 and spartalizumab treatment for potential immune-related pneumonitis

Pneumonitis (NCI-CTCAE v5.0)		
Grade	Recommended Adverse Event management guidelines	Mandatory Dose Modification requirements
Grade 1: Asymptomatic; clinical or diagnostic observations only; intervention not indicated	 Chest imaging/CT scan; repeat imaging in 3-4 weeks or as clinically indicated Monitor symptoms every 2-3 days, clinical evaluation and laboratory work-up for infection; pulse oximetry Consultation with pulmonologist recommended 	Consider interruption of spartalizumab/LAG525

Pneumonitis (NCI-CTC Grade	Recommended Adverse Event management guidelines	Mandatory Dose Modification requirements

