5.3 Laboratory parameters derivations

Grade categorization of lab values will be assigned programmatically as per NCI Common Terminology Criteria for Adverse Events (CTCAE) version 5.0. The calculation of CTCAE grades will be based on the observed laboratory values only, clinical assessments will not be taken into account. The criteria to assign CTCAE grades are given in Novartis internal criteria for CTCAE grading of laboratory parameters. The latest available version of the document based on the underlying CTCAE version 5.0 at the time of analysis will be used.

For laboratory tests where grades are not defined by CTCAEv5.0, results will be graded by the low/normal/high (or other project-specific ranges, if more suitable) classifications based on laboratory normal ranges.

A severity grade of 0 will be assigned for all non-missing lab values not graded as 1 or higher. Grade 5 will not be used. For laboratory tests that are graded for both low and high values, summaries will be done separately and labelled by direction, e.g., sodium will be summarized as hyponatremia and hypernatremia.

Table 5-3 CTC grades for laboratory values in Novartis Oncology (based on CTCAE v5.0 – Nov 2017)

Lab test (toxicity)	SI unit	Lab test (NCDS)	Normal ranges (Merck manual, July 2015) and conversion factors	CTC Grades ⁽¹⁾				
				0	1	2	3	4
Hematology								
WBC ↓ WBC (Leukocytosis)	10 ⁹ /L 10 ⁹ /L	WBC WBC	3.9 – 10.7 x 10 ⁹ /L	≥ LLN	< LLN - 3.0 x 10 ⁹ /L -	< 3.0 – 2.0 x 10 ⁹ /L -	< 2.0 – 1.0 x 10 ⁹ /L > 100 x 10 ⁹ /L	< 1.0 x 10 ⁹ /L -
Hemoglobin (Anemia) Hemoglobin ↑	g/L g/L	HGB HGB	120 - 160 g/L or 7.4 - 9.9 mmol/L (F) 140 - 170 g/L or 8.7 – 10.6 mmol/L (M) (16.113 x mmol/L = g/L)	≥ LLN	< LLN - 100 g/L < LLN - 6.2 mmol/L Increase >0-20 g/L above ULN	< 100 - 80 g/L < 6.2 - 4.9 mmol/L Increase >20-40 g/L above ULN	< 80 g/L < 4.9 mmol/L Increase >40 g/L above ULN	- - -
Platelets ↓	10 ⁹ /L	PLAT	150 - 350 x 10 ⁹ /L	≥ LLN	< LLN - 75.0 x 10 ⁹ /L	< 75.0 - 50.0 x 10 ⁹ /L	< 50.0 - 25.0 x 10 ⁹ /L	< 25.0 x 10 ⁹ /L
Neutrophils ↓	10 ⁹ /L	NEUT		≥2x10 ⁹ /L	< 2.0 - 1.5 x 10 ⁹ /L	< 1.5 - 1.0 x 10 ⁹ /L	< 1.0 - 0.5 x 10 ⁹ /L	< 0.5 x 10 ⁹ /L
Lymphocytes ↓ Lymphocytes ↑	10 ⁹ /L 10 ⁹ /L	LYM LYM		≥1.5x10 ⁹ /L	< 1.5 - 0.8 x 10 ⁹ /L -	< 0.8 - 0.5 x 10 ⁹ /L > 4 - 20 x 10 ⁹ /L	< 0.5 - 0.2 x 10 ⁹ /L > 20 x 10 ⁹ /L	< 0.2 x 10 ⁹ /L -
Biochemistry								
AST ↑	U/L	AST	0 - 35 U/L or 0 – 0.58 ukat/L (60 x ukat/L = U/L)	≤ ULN	> ULN – 3.0 x ULN	> 3.0 - 5.0 x ULN	> 5.0 - 20.0 x ULN	> 20.0 x ULN

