ALT ↑	U/L	ALT	0 - 35 U/L or 0 – 0.58 ukat/L (60 x ukat/L = U/L)	≤ ULN	> ULN – 3.0 x ULN	> 3.0 - 5.0 x ULN	> 5.0 - 20.0 x ULN	> 20.0 x ULN
Total bilirubin ↑	umol/L	BILI	5.1 – 20.5 umol/L or 0.3 – 1.2 mg/dL (17.1 x mg/dL = umol/L)	≤ ULN	> ULN - 1.5 x ULN	> 1.5 - 3.0 x ULN	> 3.0 - 10.0 x ULN	> 10.0 x ULN
Alk. Phosphatase ↑	U/L	ALP	36 - 92 U/L or 0.5 - 1.5 ukat/L (60 x ukat/L = U/L)	≤ ULN	> ULN - 2.5 x ULN	> 2.5 - 5.0 x ULN	> 5.0 - 20.0 x ULN	> 20.0 x ULN
Creatinine ↑	umol/L	CREAT	61.9 - 115 umol/L or 0.7 – 1.3 mg/dL (88.4 x mg/dL = umol/L)	≤ ULN	> ULN - 1.5 x ULN	> 1.5 - 3.0 x ULN	> 3.0 - 6.0 x ULN	> 6.0 x ULN
Creatinine kinase ↑	U/L	CK	30 - 170 U/L or 0.5 – 2.83 ukat/L (60 x ukat/L = U/L)	≤ ULN	> ULN - 2.5 x ULN	> 2.5 - 5.0 x ULN	> 5.0 - 10.0 x ULN	> 10.0 x ULN
Albumin (Hypoalbuminemia)	g/L	ALB	35 - 55 g/L or 3.5 to 5.5 g/dL	≥ LLN	< LLN - 30 g/L	< 30 - 20 g/L	< 20 g/L	-
Total Cholesterol ↑	mmol/L	CHOL	3.88 – 5.15 mmol/L or 150 - 199 mg/dL (38.67 x mg/dL = mmol/L)	≤ ULN	> ULN - 7.75 mmol/L > ULN - 300 mg/dL	> 7.75 -10.34 mmol/L > 300 – 400 mg/dL	>10.34-12.92 mmol/L > 400 – 500 mg/dL	>12.92 mmol/L > 500 mg/dL
Lipase ↑	U/L	LIPASE	<95 U/L or <1.58 ukat/L (60 x ukat/L = U/L)	≤ ULN	> ULN - 1.5 x ULN	> 1.5 - 2.0 x ULN	> 2.0 - 5.0 x ULN	> 5.0 x ULN
Amylase ↑	U/L	AMYLASE	0 - 130 U/L or 0 – 2.17 ukat/L (60 x ukat/L = U/L)	≤ ULN	> ULN - 1.5 x ULN	> 1.5 - 2.0 x ULN	> 2.0 - 5.0 x ULN	> 5.0 x ULN
Uric acid (Hyperuricemia)	umol/L	URATE	150 - 470 umol/L or 2.5 – 8 mg/dL (59.48 x mg/dL = umol/L)	Defined by clinical criteria only in CTCAE V5				

ULN = Upper Limit of Normal range; LLN = Lower Limit of Normal range

				CTC Grades ⁽¹⁾				
Lab test (toxicity)	SI unit	Lab test (NCDS)	Normal ranges (Merck manual, July 2015) and conversion factors	0	1	2	3	4
Phosphorus (Hypophosphatemia)	mmol/L	PHOS	0.97 – 1.45 mmol/L or 3.0 - 4.5 mg/dL (0.32 x mg/dL = mmol/L)	Defined by clinical criteria only in CTCAE V5				
Calcium (corrected) (Hypercalcemia)	mmol/L	CACALC	2.2 - 2.6 mmol/L or 9 - 10.5 mg/dL (0.2495 x mg/dL = mmol/L)	≤ ULN	> ULN - 11.5 mg/dL > ULN - 2.9 mmol/L	> 11.5 - 12.5 mg/dL > 2.9 - 3.1 mmol/L	> 12.5 - 13.5 mg/dL > 3.1 - 3.4 mmol/L	> 13.5 mg/dL > 3.4 mmol/L
Calcium (corrected) (Hypocalcemia)	mmol/L	CACALC		≥ LLN	< LLN - 8.0 mg/dL < LLN - 2.0 mmol/L	< 8.0 - 7.0 mg/dL < 2.0 - 1.75 mmol/L	< 7.0 - 6.0 mg/dL < 1.75 - 1.5 mmol/L	< 6.0 mg/dL < 1.5 mmol/L

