Values and LNRs for blood differentials can be given as %, absolute values should then be calculated using WBC. Generally, ≥ 1.5 x 10⁹/L (lymphocytes) and ≥ 2 x 10⁹/L (neutrophils) are considered as LAB CTC grade 0

The comparison with baseline is not considered for derivation of LAB CTC grades

Imputation Rules

CTC grading for blood differentials is based on absolute values. However, this data may not be reported as absolute counts but rather as percentage of WBC.

If laboratory values are provided as '<X' (i.e. below limit of detection) or '>X', prior to conversion of laboratory values to SI unit, these numeric values are set to X.

The following rules will be applied to derive the WBC differential counts when only percentages are available for a xxx differential

$$\text{xxx count} = (\text{WBC count}) * (\text{xxx \%value} / 100)$$

Further derivation of laboratory parameters might be required for CTCAE grading. For instance, corrected calcium can be derived using the reported total calcium value and albumin at the same assessment using the following formula:

$$\text{Corrected Calcium (mg/dL)} = \text{Calcium (mg/dL)} - 0.8 [\text{Albumin (g/dL)} - 4]$$

In order to apply the above formula, albumin values in g/L will be converted to g/dL by multiplying by 0.1, calcium values in mmol/L will be converted to mg/dL by dividing by 0.2495. For calculation of laboratory CTC grades 0 and 1, the normal range for derived corrected calcium is set to the same limits (in mg/dL) as for calcium.

CTC grades for the derived absolute WBC differential counts (neutrophils, lymphocytes) and corrected calcium will be assigned as described above for grading.

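### The SAP grades creatinine against ULN only, while the protocol's CTCAE v5.0 nephritis table also grades it against baseline, so some Grade 2 and 3 rises are under-graded in the programmed laboratory tables

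*SAP*

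**What the plan says.** SAP 5.3 states the standard: "Grade categorization of lab values will be assigned programmatically as per NCI Common Terminology Criteria for Adverse Events (CTCAE) version 5.0". Protocol 12.5.2 says the same for laboratory values and sets aside only clinical assessments.

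SAP Table 5-3 then defines every creatinine grade by ULN alone: Grade 0 up to ULN, Grade 1 to 1.5 x ULN, Grade 2 to 3.0 x ULN, Grade 3 to 6.0 x ULN, and Grade 4 above that. A note under the table applies to all parameters: "The comparison with baseline is not considered for derivation of LAB CTC grades".

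Protocol Table 6-6, the nephritis table in section 6.5.1.2, cites CTCAE v5.0 in its title row. Its lowest grade matches the SAP: "Grade 1: Creatinine >ULN to ≤1.5x ULN". The next two grades do not, because each carries a baseline criterion beside the ULN criterion: "Grade 2: Creatinine >1.5 - 3.0 x baseline; >1.5 to ≤ 3.0 x ULN" and, for the next grade, "Grade 3: Creatinine >3.0 x baseline", followed by its own ULN range. The table attaches dose interruption to Grade 2 and permanent discontinuation to Grade 3, and section 6.5.1.2.1 calls the dose-modification column mandatory.

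SAP 2.9.3 uses the programmed grade in the worst post-baseline grade table, the shift tables and the listing of Grade 3 or 4 laboratory toxicities. SAP section 4 lists no change to protocol-specified analyses.

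**The concern.** Both documents invoke the same CTCAE version, yet they can give different grades to the same creatinine value in the same participant. The difference runs one way: dropping the baseline criterion can lower a grade but cannot raise it. A rise that Table 6-6 ties to interruption or discontinuation may therefore appear in the laboratory tables at a lower grade, and a Grade 3 rise may be missing from the Grade 3/4 listing.

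Changes in chemistry values are part of a stated secondary safety endpoint, and the amended SAP serves a close-out report on safety and PK. A reader of that report would take the laboratory grades to be CTCAE v5.0 grades as the protocol displays them.

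**Working it through.** There is no stated figure to reproduce, because this is a grading rule. The check compares the two rules directly.

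**Inputs.** SAP Table 5-3 gives a reference range of 61.9 to 115 µmol/L. Its unit conversion agrees: 0.7 x 88.4 = 61.9 and 1.3 x 88.4 = 114.9. The SAP grade limits are 1, 1.5, 3 and 6 x ULN. The Table 6-6 baseline limits are 1.5 and 3.0 x baseline. Let b be baseline and x the later value.

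**Rules.** The SAP grade depends on x/ULN only. The Table 6-6 grade is the higher of the ULN grade and the baseline grade, which is Grade 2 if 1.5b < x ≤ 3b and Grade 3 if x > 3b.

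**Where they differ (ULN 115).**

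| Table 6-6 grade | SAP grade | Possible when | Baseline limit, µmol/L |
|---|---|---|---|
| 2 | 1 | 1.5b < 1.5 x ULN and 3b > ULN | below 115 (and above 38.3) |
| 2 | 0 | 1.5b < ULN | below 115/1.5 = 76.7 |
| 3 | 2 | 3b < 3 x ULN | below 115 |
| 3 | 1 | 3b < 1.5 x ULN | below 115/2 = 57.5 |
| 3 | 0 | 3b < ULN | below 115/3 = 38.3 |

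The last two rows need a baseline under the quoted lower limit of 61.9. Within the quoted range, a Grade 3 rise on the baseline criterion alone shows as Grade 2.

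**Bands at a baseline of 62 µmol/L.** 1.5 x 62 = 93; 3 x 62 = 186; 1.5 x 115 = 172.5; 3 x 115 = 345.
- Above 93 to 115: Table 6-6 Grade 2, SAP Grade 0.
- Above 115 to 172.5: Grade 2 against Grade 1.
- Above 172.5 to 186: Grade 2 under both.
- Above 186 to 345: Grade 3 against Grade 2.

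**Single cases (ULN 115).**

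| Baseline to value | x/b | x/ULN | Table 6-6 | SAP |
|---|---|---|---|---|
| 61.9 to 100 | 1.62 | 0.87 | 2 | 0 |
| 80 to 150 | 1.88 | 1.30 | 2 | 1 |
| 61.9 to 190 | 3.07 | 1.65 | 3 | 2 |
| 110 to 335 | 3.05 | 2.91 | 3 | 2 |
| 115 to 175 | 1.52 | 1.52 | 2 | 2 |

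Over a grid of baselines from 20 to 299 and values from 20 to 899 µmol/L, the SAP grade never exceeded the Table 6-6 grade. With baseline at or above ULN the two agree.

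**Sensitivity to ULN.** The study laboratories' ULNs are not given, so this range is assumed.

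| ULN | Grade 2 shown as 0 if baseline below | Grade 3 shown as 1 if baseline below |
|---|---|---|
| 80 | 53.3 | 40.0 |
| 90 | 60.0 | 45.0 |
| 100 | 66.7 | 50.0 |
| 115 | 76.7 | 57.5 |

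At ULN 80 and baseline 62 the Grade 0 band disappears, because 93 already exceeds ULN. The Grade 3 gap shrinks from 186-345 to 186-240 (3 x 80 = 240). The direction does not change.

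**The case against.** The strongest reply is that the two tables do different jobs. Table 6-6 governs dosing for potential immune-related nephritis. The laboratory tables are descriptive, are graded by program from observed values, and follow a convention that the SAP states openly. Nothing in the protocol says that they must reproduce Table 6-6. This stands as far as it goes, and it limits the weight of the point. It does not remove the conflict: both documents claim CTCAE v5.0, protocol 12.5.2 sets aside clinical assessments but not baseline, and SAP section 4 declares nothing. Baseline-referenced grading is not foreign to the SAP either, since the ejection-fraction shift table in 2.9.4.1 uses drops from baseline.

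Rises that were acted on also have other reporting routes. Abnormal values that are clinically significant or need therapy are AEs (protocol 10.1.1). AEs are assessed separately under CTCAE v5.0 (SAP 5.2), nephritis AESIs are built from MedDRA terms (SAP 2.9.1.1), and all laboratory values are listed. This is correct. A reader might infer that nephritis AESIs are under-counted, and the documents do not support that.

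The 61.9-115 range is a general reference range printed in the table, and the study laboratories may differ. This also stands, and is why a range of ULNs is shown.

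Finally, the footnote covers every parameter, and protocol Table 6-4 also refers to baseline for liver tests when baseline is abnormal. Changing creatinine alone gives a mixed convention, so the SAP should say plainly which parameters are exempt.

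**Conclusion.** The inconsistency is real and the under-grading runs in one direction. It arises when baseline is below ULN and a value meets the baseline criterion but not the ULN criterion for the same grade. Table 6-6 Grade 2 then becomes Grade 1, or Grade 0 for baselines under ULN/1.5. For a baseline in the quoted normal range, Grade 3 becomes Grade 2 and is lost from the Grade 3/4 listing. The effect is confined to the three programmed laboratory outputs.

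Two stronger readings are tempting. One is that discontinuation-level rises can appear as Grade 0. At ULN 115 that needs a baseline below 38.3 µmol/L, well under the quoted lower limit, so Grade 0 is realistic only for Grade 2 rises. The other is that the under-count concentrates in the carboplatin arms. The rule is identical in all arms, protocol 1.1.3.4 calls carboplatin's nephrotoxic potential limited, and no data show a concentration.

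The conclusion rests on reading the semicolon in Table 6-6 as 'or', which the protocol does not state, and on taking that table's CTCAE v5.0 label at face value. The documents contain no creatinine data, so the number of participants affected cannot be computed. The point deserves correction but does not touch the efficacy conclusions.

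**What to change.** Change the analysis only. For creatinine, tabulate the higher of the ULN-based grade and the baseline-based grade already shown in Table 6-6, using the safety baseline defined in SAP 2.1.1. Reword the Table 5-3 footnote so that it no longer covers creatinine, and keep the ULN-only table alongside for comparison with the sponsor's standard outputs.

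At minimum, add a table of each participant's worst on-treatment creatinine ratio to baseline, with the counts above 1.5 and above 3.0, and record the departure from the Table 6-6 grading in SAP section 4.

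The cost is SAP wording and minor programming, with no new data. The downside is that counts of graded creatinine increase will rise and will differ from the sponsor's standard tables. No clinical threshold is proposed here; the SAP and protocol passages should be reconciled.

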5.4 Statistical models

5.4.1 Primary analysis

Analysis of Binary Data

Dual-criterion based Proof of Concept designs

The two criteria to assess the proof of preliminary efficacy (PPE) in each treatment group are thus:

- Clinical relevance: posterior mean $\geq 35\%$
- Bayesian statistical significance: $\text{pr}(\text{ORR} \geq 25\% \mid \text{data}) \geq 0.90$

Let p_i denote the ORR for treatment group i and which follows a beta prior distribution Beta $[a, b]$, where $a > 0$, $b > 0$. Let y_i out of n_i subjects be responders. Therefore, the posterior distribution of p_i is Beta $(a + y_i, b + n_i - y_i)$ [Spiegelhalter et al. 2004].

A minimally informative unimodal Beta prior [Neuenschwander et al. 2008] Beta $[0.35/(1-0.35), 1]$ will be used. The parameters were chosen so that the mean of the prior distribution is equal to 0.35, which ensures that the clinical relevance criterion is met, if the observed ORR is exactly equal to 35%.

The efficacy criteria will be assessed based on the actual number of subjects enrolled in the study. For example, if the total number of subjects is 32 in a given treatment group, the first efficacy criterion requires that at least 12 subjects are responders. In that case, the posterior distribution is Beta $(0.35/(1-0.35)+12, 1+32-12)$ and the posterior probability $\text{pr}(\text{ORR} \geq 25\% | \text{data}) = 0.939$.

For further details, see [Appendix 2 of the study protocol](#).

Confidence interval for response rate

Responses will be summarized in terms of percentage rates with 95% confidence intervals using exact binomial confidence interval (implemented using SAS procedure FREQ with EXACT statement for one-way table [[Clopper and Pearson 1934](#)]).

Analysis of time to events Data

Kaplan-Meier estimates

An estimate of the survival function in each treatment group will be constructed using Kaplan-Meier (product-limit) method as implemented in PROC LIFETEST with METHOD=KM option. The PROC LIFETEST statement will use the option CONFTYPE=LOGLOG.

Median survival for each treatment group will be obtained along with 95% confidence intervals calculated from PROC LIFETEST output using the method of [[Brookmeyer and Crowley 1982](#)]. Kaplan-Meier estimates of the survival function with 95% confidence intervals at specific time points will be summarized. The standard error of the Kaplan-Meier estimate will be calculated using Greenwood's formula [[Collett 1994](#)].

Treatment of ties

The STRATA statement in LIFETEST procedure will be used to analyze time to event data with ties.

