Variable (or endpoint)	The variable (or endpoint) to be obtained for each participant that is required to address the clinical question. The specification of the variable might include whether the participant experiences an intercurrent event.
Withdrawal of study Consent (WoC)	Withdrawal of consent from the study occurs only when a participant does not want to participate in the study any longer, and does not allow any further collection of personal data

Amendment 4 (15-Feb-2021)

At the time of amendment 4, 20 participants have been randomized to treatment Arm 1, 34 participants have been randomized to treatment Arm 2, and 34 participants have been randomized to treatment Arm 3. Of the 88 randomized participants, 85 participants have discontinued the study treatment. Three participants are still receiving treatment in Arm 2 (LAG525 + spartalizumab + carboplatin), 3 participants are in safety follow-up (of which one is still in efficacy follow-up) and 12 are in survival follow-up.

Amendment rationale

The primary efficacy analysis was performed with a data cut-off date of 27-Feb-2020. None of the three treatment arms met the proof of preliminary efficacy (PPE) criteria of a mean of the posterior distribution of $ORR \ge 35\%$ and a posterior probability of $(ORR \ge 25\%) > 90\%$. No new safety signals were identified for any of the treatment arms.

Based on these results and together with an increasingly crowded treatment landscape in metastatic TNBC, Novartis decided to not further develop LAG525 in TNBC. This decision is not due to safety concerns.

The main purpose of this amendment is to: 1) define the duration of the follow-up period and 2) clarify the trial discontinuation rules for participants who are still ongoing in the trial as to whether they are eligible for a Post Trial Access (PTA) program i.e. rollover protocol or a post study drug supply (PSDS).

The following modifications were incorporated:

- The survival follow-up period will be removed and participants who are currently in survival follow-up can discontinue from the study with approval of amendment 4.
- The post treatment follow-up period will be limited to the safety follow-up period of 150 days after the last dose of LAG525 and/or spartalizumab (whichever was stopped last). If carboplatin was stopped more than 150 days after LAG525 and/or spartalizumab, the participant can be discontinued 30 days after the last dose of carboplatin.

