16.2 Appendix 2: Statistical considerations

The primary endpoint is the overall response rate (ORR). The analysis of the primary endpoint, which is Bayesian, uses a binomial sampling and a Beta prior distribution.

Based on clinical discussions and available literature, the null value for the ORR was set to 25%. Moreover, a minimum ORR improvement of 10% was considered necessary to justify further development (see Section 12.4.2 for information on published data available to help elicit the 25% and 35% targets).

The two criteria to assess the proof of preliminary efficacy (PPE) in each treatment group are thus:

- Clinical relevance: posterior mean ≥ 35%
- Bayesian statistical significance: $pr(ORR \ge 25\% \mid data) \ge 0.90$

The first criterion is met if the posterior mean ORR is at least 35% which is the minimum ORR of clinical interest. The second criterion provides reasonable evidence that the posterior ORR is better than the null value of 25%. Both criteria need to be met by at least one treatment group in order to meet the primary objective of the study.

Each analysis by treatment group is performed separately using a Beta-binomial model as follows:

Let us assume that y_i out of n_i patients have a response as per ORR in treatment group i (either LAG525 + spartalizumab, LAG525 + spartalizumab + carboplatin or LAG525 + spartalizumab + carboplatin).

The likelihood function is $y_i \sim Bin(n_i, p_i)$ where p_i denotes the ORR for treatment group i.

Assume p_i follows a beta prior distribution: $[p_i] \sim \text{Beta}(a_i, b_i)$, where $a_i > 0$, $b_i > 0$

The posterior distribution of p_i is therefore: $[p_i | y_i] \sim \text{Beta}(a_i + y_i, b_i + n_i - y_i)$

A minimally informative prior with unimodal Beta(0.35/(1-0.35),1) distribution is used. The prior parameters are chosen so that the prior mean for ORR is equal to 35%. This ensures that the clinical relevance criterion is met, if the observed ORR is exactly equal to 35%.

With the two criteria stated above the minimally required sample size is 32.

To better understand the design, operating characteristics for various true ORR were assessed using simulations as follows:

- Generate 100,000 trials with ORR results (yes / no) for n_i participants per treatment group, where the ORR follows a binomial distribution $y_i \sim Bin(n_i, p_i)$.
- Evaluate for each of these simulated trials whether the PPE criteria are met.

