2.2 Analysis sets

Full Analysis Set

The Full Analysis Set (FAS) comprises all subjects to whom study treatment has been assigned by randomization. According to the intent to treat principle, subjects will be analyzed according to the treatment and strata they have been assigned to during the randomization procedure.

Safety set

The Safety Set includes all subjects who received at least one dose of study treatment (i.e., at least one dose of any component of the study treatment, including incomplete infusion of spartalizumab, LAG525 or carboplatin). Subjects will be analyzed according to the study treatment received, where treatment received is defined as the randomized treatment if the subject took at least one dose of that treatment or the first treatment received if the randomized treatment was never received.

Pharmacokinetic analysis set (PAS)

The LAG525 pharmacokinetic analysis set (**PAS-LAG525**) includes all subjects who provide at least one evaluable LAG525 PK concentration. For a concentration to be evaluable, subjects are required to:

- Receive a planned dose of LAG525 prior to sampling.
- For pre-dose samples: have the sample collected prior to dosing on the assessment day and for samples post-C1D1 have the sample collected approximately 504 hr \pm 24 hours after the previous dose.
- For end-of-infusion samples: have the sample collected 1 hour post end of infusion within \pm 5 minutes of the scheduled time point;
- For 168 and 336 hours samples: have the sample collected 168, 336 hours post end of infusion within \pm 24 hours of the scheduled timepoint.

The spartalizumab pharmacokinetic analysis set (**PAS-Spartalizumab**) includes all subjects who provide at least one evaluable Spartalizumab PK concentration. For a concentration to be evaluable, subjects are required to:

- Receive a planned dose of spartalizumab prior to sampling.
- For pre-dose samples: have the sample collected prior to dosing on the assessment day and for samples post-C1D1 have the sample collected approximately 504 hr \pm 24 hours after the previous dose.
- For end-of-infusion samples: have the sample collected 1 hour post end of infusion within \pm 5 minutes of the scheduled time point; have the sample collected 168, 336 hours post end of infusion within \pm 24 hours of the scheduled timepoint.

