3.1 Primary analysis

The sample size calculation is based on the primary variable ORR considering the statistical model, hypothesis and method of analysis detailed in [Section 2.5](#). Proof of preliminary efficacy (PPE) for each drug combination (study arm) will be declared if both of the following conditions are met:

- the mean of the posterior distribution of ORR is at least 35%
- and
- the posterior probability that the ORR is $\geq 25\%$ is at least 0.9

Approximately 32 subjects will be enrolled in each arm for a total of approximately 96 subjects. In a given arm of 32 subjects, the type-I error rate is 8% while the probability of declaring proof of preliminary efficacy (PPE) is at least 80% for ORR $\geq 45\%$ ([Table 3-1](#)).

Table 3-1 Operating characteristics with 32 subjects in each arm

True ORR	Probability of declaring PPE in each arm (12 or more responders)	Probability of missing PPE (11 or less responders) in each arm
25 %	0.079	0.921
30 %	0.228	0.772
35 %	0.448	0.552
40%	0.675	0.325
45 %	0.847	0.153

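### The quoted 8% type-I error belongs to arms of 32; at the 34 randomized to each of Arms 2 and 3 the bar is still 12 responders and the rate is 11.9%

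*SAP*

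**What the plan says.** **Rule.** SAP 3.1 declares PPE in an arm when two conditions hold. The first is that "the mean of the posterior distribution of ORR is at least 35" percent. The second concerns "the posterior probability that the ORR is" 25% or more, which must reach 0.9. Protocol Appendix 2 (16.2) states that "the null value for the ORR was set to 25" percent. Under SAP 2.5.2, PPE in any one arm makes the study positive.

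**Prior.** Beta(0.35/0.65, 1). SAP 5.4.1 explains: "The parameters were chosen so that the mean of the prior distribution is equal to 0.35". The stated purpose is that an observed ORR of exactly 35% should satisfy the first condition.

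**Quoted error rate.** SAP 3.1: "In a given arm of 32 subjects, the type-I error rate is 8" percent. Protocol 12.8.1 gives the same figure. Protocol Appendix 2 adds rows for 36 and 40 participants; neither document has a row for 34.

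**Sample size the rule is applied to.** SAP 5.4.1: "The efficacy criteria will be assessed based on the actual number of subjects enrolled in the study". SAP 2.2: "The Full Analysis Set (FAS) comprises all subjects to whom study treatment has been assigned by randomization". The status paragraph of protocol Amendment 4 reports that "34 participants have been randomized to treatment Arm 2, and 34 participants have been randomized to treatment Arm 3".

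**Text not updated.** SAP 3.1 still plans about 32 per arm and about 96 overall, and SAP 1.1 also gives about 96. The SAP introduction says the plan is based on protocol version 04, which carries the 34/34 count.

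**The concern.** The error rate is quoted at the planned size, while the decision is made at the achieved size. With a binary endpoint and a whole-number bar the two can differ noticeably, because the error rate climbs as participants are added until the bar moves up by one responder.

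A reader taking the protocol's tabulated null values (0.079 at 32, 0.092 at 36) and interpolating would expect 8% to 9% at 34. If the true figure lies outside that range, the SAP and any report that repeats its design section would credit Arms 2 and 3 with a false-positive rate they do not have. Because a single arm can make the study positive, the per-arm rate is the one that matters.

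**Working it through.** **Inputs.** Null ORR 25% (protocol Appendix 2). Prior Beta(a, 1) with a = 0.35/0.65 = 0.5385 (SAP 5.4.1). Two criteria (SAP 3.1). Planned n = 32 (SAP 3.1). Achieved n = 34 in each of Arms 2 and 3 (protocol Amendment 4), with all randomized participants as the analysis set (SAP 2.2).

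**Formulas.** With y responders out of n, the posterior is Beta(0.5385 + y, 1 + n − y).

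- Criterion 1: (0.5385 + y)/(1.5385 + n) ≥ 0.35. Since 0.35 × 1.5385 = 0.5385, this reduces to y ≥ 0.35n.
- Criterion 2: the posterior probability that ORR ≥ 0.25 is at least 0.90.
- The bar c is the smallest y meeting both. P(declare PPE) = Σ from k = c to n of C(n,k) p^k (1−p)^(n−k).

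**Step 1: reproduce the plan's figure at n = 32.** 0.35 × 32 = 11.2, so criterion 1 needs 12. At 12/32 the posterior mean is 12.5385/33.5385 = 0.374 and the posterior probability is 0.9385 (SAP: 0.939). The bar is 12.

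| True ORR | Exact, n = 32 | Plan's table |
|---|---|---|
| 25% | 0.0804 | 0.079 |
| 30% | 0.2283 | 0.228 |
| 35% | 0.4485 | 0.448 |
| 40% | 0.6767 | 0.675 |
| 45% | 0.8487 | 0.847 |

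The plan's values come from 100,000 simulated trials. The standard error at the null is √(0.0804 × 0.9196/100,000) = 0.0009, so the table is reproduced within simulation error.

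**Step 2: the bar at n = 34.** 0.35 × 34 = 11.9, so criterion 1 still needs 12.

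- 12/34: posterior mean 12.5385/35.5385 = 0.3528; posterior probability 0.9063. Both criteria met.
- 11/34: posterior mean 11.5385/35.5385 = 0.3247; posterior probability 0.8288. Both fail.

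**Step 3: operating characteristics at n = 34, bar 12.**

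| True ORR | P(declare PPE) | P(miss PPE) |
|---|---|---|
| 25% | 0.119 | 0.881 |
| 30% | 0.307 | 0.693 |
| 35% | 0.550 | 0.450 |
| 40% | 0.767 | 0.233 |
| 45% | 0.906 | 0.094 |

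**Step 4: why 34 is not covered by the tabulated sizes.**

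| n | 0.35n | Bar | Exact type-I error | Plan's table |
|---|---|---|---|---|
| 32 | 11.20 | 12 | 0.0804 | 0.079 |
| 33 | 11.55 | 12 | 0.0987 | none |
| 34 | 11.90 | 12 | 0.1193 | none |
| 35 | 12.25 | 13 | 0.0756 | none |
| 36 | 12.60 | 13 | 0.0922 | 0.092 |
| 40 | 14.00 | 14 | 0.1032 | 0.102 |

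The sequence is a sawtooth, and 34 is the last size before the bar rises to 13. Its error rate is above all three tabulated values, so interpolation misses it.

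**Step 5: is the prior responsible?** The observed rate 12/34 = 35.3% is already above 35%. Other weak priors also pass 12/34, and so give the same 11.9%:

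- Beta(1,1): mean 0.3611, probability 0.9244.
- Beta(0.5,0.5): mean 0.3571, probability 0.9136.
- Mean 0.25 and total weight 0.25: mean 0.3522, probability 0.9005.

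**The case against.** **The 8% is not a mistake.** It is stated for an arm of 32 and reproduces exactly there. SAP 5.4.1 says openly that the rule uses the actual number and presents 32 as an example. Protocol Appendix 2 shows that the rate varies with n. All of this stands, and anyone who infers a miscalculation is wrong. What it leaves open is that no document gives the rate at 34, and none of the tabulated rates is as high as 11.9%.

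**The prior.** A reader might infer that centring the prior on the 35% target, rather than on the 25% null, inflates the error rate or decides the outcome at exactly 12 responders. The documents do not support that. Their stated reason for the prior is that an observed 35% should meet the first criterion, and 12/34 exceeds 35% without help. Flat, Beta(0.5,0.5) and very lightly weighted null-centred priors also pass 12/34. A null-centred prior with somewhat more weight does move the bar: at total weights from 0.5 to 10, 12/34 fails and 13 are needed, with type-I error 6.1%. That shows only that a stricter prior gives a stricter rule. The rise from 8.0% to 11.9% comes from two more participants with the bar unchanged at 12.

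**Nothing turns on it now.** Amendment 4 reports that no arm met the PPE criteria at the primary analysis, and the SAP introduction says this version was amended for a close-out report with no inferential analysis. A false-positive rate bears on a positive declaration, and there was none. This stands too, and it is why the point is minor.

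**Conclusion.** The point holds as a correction to a reported design property. For Arms 2 and 3 the exact per-arm type-I error is 11.9%, not 8%: 0.1193/0.0804 = 1.48, or about half as high again. The PPE probability at the achieved size is also higher than tabulated for 32: 55.0% against 44.8% at a true ORR of 35%, and 90.6% against 84.7% at 45%.

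This assumes that all 34 randomized participants per arm are in the analysis set. SAP Table 2-2 allows exclusion only for missing written consent. One such exclusion would give n = 33 and 9.9%; two would return the arm to 32 and 8.0%. It also assumes a common response probability within an arm, as the plan's own calculation does.

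A reader might infer that the higher error rate casts doubt on the trial's conclusion. It does not: every arm failed the rule, so there is no positive declaration to question. Severity is minor.

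**What to change.** Add an n=34 row set (Step 3) to the operating characteristics in SAP 3.1, protocol 12.8.1 and protocol Appendix 2. Quote 11.9% as the type-I error for Arms 2 and 3, keeping 8% as the planned value for 32. Update the SAP text that still gives 32 per arm and about 96 in total so that it matches the achieved numbers. Carry the n=34 figures into any study report that describes the design's error rate.

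No change to the prior or the decision rule is needed, and no extra prior-sensitivity analysis. The cost is a few lines of text and one set of table rows, with no new data. The only downside is that the quoted error rate looks less favourable.
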